7.3.	2 Measuring autophagy induction and autophagy inhibition in tumor tissue.	25
7.3.	3 Therapy-induced aene expression changes in the tissue microenvironment	25
7.4	BI OOD BASED CORRELATIVE STUDIES.	25
7.4	1 Plasma biomarkers for autophaav dynamics.	25
74	2 Methods for Collecting Plasma	26
74	3 FEPE archival tumor tissue for genetic analysis	27
8.0 9.4	TUDY CALENDAR	28
9.0	MEASUREMENT OF EFFECT	31
91	DEFINITIONS	31
9.2	DISEASE PARAMETERS	31
93	METHODS FOR EVALUATION OF MEASURABLE DISEASE	32
9.4		32
9.4 9.4	1 Evaluation of Taraet Lesions	32
9.4. 9.4	 Evaluation of Non-Taraet Lesions 	32
5.4.		

9.4.3	Evaluation of Best Overall Response	.33
9.4.4	Duration of Response	.34
9.4.5	Progression-Free Survival	.34
9.4.6	Overall Survival	. 34
9.4.7	' Off treatment/Off Study	.34
10.0 AI	DVERSE EVENTS AND REPORTING	.34
10.1	Adverse Events	.35
10.2	RECORDING OF ADVERSE EVENTS.	.35
10.2.	1 Serious Adverse Events	.36
10.3	ASSESSMENT OF ADVERSE EVENTS	.36
10.3.	1 Relationship to study drug: Yes	.37
10.3.	2 Relationship to study drug: No	.37
10.3.	3 Diagnosis vs. Signs and Symptoms	.38
10.3.	4 Deaths	. 38
10.3.	5 Preexisting Medical Conditions	.38
10.3.	6 Pregnancy	. 38
10.4	SAE REPORTING TO ARRAY	.38
10.5	UPENN IRB NOTIFICATION BY INVESTIGATOR-SPONSOR	.39
10.5.	1 Reporting Process to IRB at Penn.	.41
10.5.	2 FDA Notification by Investigator-Sponsor.	.41
10.6	MEDICAL MONITORING	.41
10.7	STUDY MONITORING PLAN	.41
10.8	AUDITING AND INSPECTING	.41
11.0 ST	ATISTICAL CONSIDERATIONS	.42
11.1	DESIGN	.42
11.2	OBJECTIVES	.42
11.3	ENDPOINTS	.42
11.4	SIMON 2-STAGE DESIGN	.43
11.5	PLANS FOR DATA ANALYSIS	.43
11.6	SAMPLE SIZE	.44
11.7	STUDY DURATION	.44
REFERENC	ES	.45
APPENDIX	A: ECOG PERFORMANCE STATUS	.47
APPENDIX	B: DEFINITION OF NON-CHILDBEARING POTENTIAL AND MEDICALLY ACCEPTABLE METHODS OF	
BIRTH COI	NTROL	.48

STUDY SUMMARY

Title	The LIMIT KRAS Mutant NSCLC Trial: Lysosome Inhibition to Enhance MAPK Inhibition Targeting KRAS Mutant NSCLC: A Phase 2 Open Label Trial of Binimetinib and Hydroxychloroquine in Patients with Advanced KRAS Mutant Non-Small Cell Lung Cancer				
Protocol Number	UPCC 21520				
Phase	Phase 2				
Methodology	Single Arm				
Study Duration	2 years				
Study Center(s)	Single Center Primary Objectives				
	 Determine the Objective Response Rate (ORR) of binimetinib (B) and hydroxychloroquine(HCQ), as measured by RECIST 1.1 Determine the safety/tolerability of B+ HCQ, as measured by CTCAE 5.0 				
Objectives	 Secondary Objectives Progression-Free Survival Overall Survival Measurement of changes in circulating tumor DNA (ctDNA) KRAS allelic frequency Measurement of changes in biomarkers related to autophagy 				
Number of Subjects	 Stage 1: 10 patients Stage 2: 19 patients Total: Up to 29 patients Must be ≥ 18 years of age. Metastatic or incurable NSCLC Presence of a non-synonymous mutation in KRAS Must have received at least one prior systemic therapy for metastatic NSCLC, or be intolerant/otherwise ineligible for such therapy 				
Diagnosis and Main Inclusion/Exclusion Criteria	 Must have ECOG performance status of 0 or 1 Must have adequate renal, liver, cardiac and hematological function Must be able to provide written informed consent. Must have at least one measurable lesion according to Response Evaluation Criteria for Solid Tumors (RECIST 1.1) Patients with asymptomatic or treated, stable brain metastases are allowed to enroll. Patients with carcinomatous meningitis are excluded. 				

Study Product, Dose, Route, Regimen	Hydroxychloroquine 400 mg by mouth every 12 hours (obtained commercially), binimetinib 45 mg 2 times daily				
Duration of administration	Until progression, unacceptable toxicity, or withdrawal of consent.				
Study design	Phase 2: Optimal Simon 2-stage design with the first stage recruiting 10 patients, and 19 additional patients if there are ≥ 2 responses seen.				
Duration of trial	 Approximately 2 years Follow-up: All subjects will be evaluated per study calendar for 6 months after discontinuation of study treatment All subjects will be followed for a minimum of one year from the start of treatment, unless disease progression is reported prior to one year. 				

1.0 OBJECTIVES

1.1 Primary Objectives

- To assess the clinical efficacy of HCQ + B by ORR.
- Determine the safety/tolerability of HCQ + B as measured by CTCAE 5.0.

1.2 Secondary Objectives

- To measure the progression-free survival among patients treated with HCQ+B
- To measure the overall survival among patients treated with HCQ+B.

1.3 Correlative Objectives

- To evaluate the correlation between response to HCQ + B and pre-treatment tumor staining for PPT1, LC3, ALDH1A1, and HLTF by immunohistochemistry.
- To monitor changes on a repeat biopsy after 3 weeks of treatment with HCQ + B in PPT1, LC3, ALDH1A1, and HLTF by immunohistochemistry, as well as in gene signatures.
- To measure the change in median number of autophagic vesicles/cell (mAV/cell) in serially collected tumor tissue with HCQ + B.
- To determine if blood based candidate biomarkers of autophagy modulation (including IL-8, Interleukin-1 Beta, LIF, DKK3, and FAM3C, and other serum cytokines) reflect autophagy dynamics in tumors of patients treated with HCQ + B.
- To characterize HCQ pharmacokinetics when HCQ is combined with binimetinib
- To monitor changes in allelic fraction of KRAS in circulating tumor DNA (ctDNA) among patients treated with HCQ + B

2.0 BACKGROUND AND RATIONALE

2.1 Patient population

Non-small cell lung cancer (NSCLC) is the leading cause of cancer death for both men and women in the United States. The use of targeted therapy based on molecular profile has completely changed the treatment approach for patients with genetic alterations in the EGFR, ALK, and ROS1 genes. Such patients are now routinely treated with tyrosine kinase inhibitors(TKIs), and the overall survival seen in these patient populations is substantially longer than the general population of patients with NSCLC. Despite being the most commonly mutated gene in non-squamous NSCLC, KRAS has been historically very difficult to target. The relative resistance of *KRAS* mutant NSCLC to TKI based therapy is likely related to the very strong affinity of KRAS for its natural ligand. While there have been some emerging advances for *KRAS* G12C mutant NSCLC using allosteric inhibitors, there have been nearly no advances in the targeted therapy of patients with other *KRAS* mutations.

2.2 Rationale for combined Lysosomal and Autophagy inhibition

The lysosome has been found to be critical for the growth of pancreatic cancer (Perera Nature PMC5086585). Kimmelman's group has published multiple papers demonstrating that autophagy is critical for pancreatic cancer growth and targeting with chloroquine derivatives produces cytotoxicity in most pancreatic cancer cell lines and patient derived xenografts (Yang Cancer Discovery 2014; PMC4125497). The University of Pittsburgh group has done extensive preclinical and clinical work on combining HCQ with chemotherapy. A phase I/II trial of 35 patients examined the neoadjuvant treatment with HCQ and gemcitabine in patients with borderline resectable pancreatic adenocarcinomas (Boone Annals of Surgery 2015; PMC4663459). 1200 mg/day of HCQ was taken for 31 days up until the day of surgery combined with two doses of a fixed-dose 1500 mg/m² gemcitabine. DLT or grade 4/5 events did not occur during this trial. 19/35 patients had a decrease in surrogate biomarker response (CA 19-9) and 29/35 patients underwent surgical resection as scheduled. This trial demonstrated that HCQ with gemcitabine is safe and tolerable, and showed encouraging activity in the neoadjuvant setting. A randomized phase II trial with gemcitabine, abraxane, with or without HCQ in resectable pancreatic cancer patients has been launched (NCT01978184), and a randomized phase II study of gemcitabine, abraxane, with or without HCQ in the metastatic setting (NCT01506973) found that HCQ added to chemotherapy significantly improved response rate (Karasic JAMA Oncology 2019; PMC6547080). The safety and activity of combining dabrafenib (BRAF inhibitor) trametinib (MEK inhibitor) and HCQ has been preliminarily demonstrated in an ongoing Phase I/II trial in BRAF mutant melanoma patients (See below).

Recently published data supporting MEK inhibitor + HCQ combination for *Ras* mutant cancer. Three separate teams of investigators at the University of Utah, University of North Carolina Chapel Hill/NYU, and NCI/UCSF have found stunning activity of combining HCQ with either MEK (University of Utah) or ERK inhibition (UNC) in preclinical models of *KRAS*-driven pancreas cancer. The Utah group included melanoma colon and lung cancer xenografts with *RAS* mutations. In all cases the combination of a MEK inhibitor with HCQ was synthetically lethal to *RAS* mutant cancers, with tumors regressing in each case (Kinsey Nature Medicine 2019 PMID:30833748; Bryant Nature Medicine 2019 PMID:30833752; Lee PNAS 2019 PMC6410784). This data provides the rationale for studying a MEK inhibitor in combination with HCQ in *KRAS* mutant non-small cell lung cancer.

2.3 Binimetinib

Binimetinib (also known as MEK162, ARRY-438162 or ONO-7703) is an orally bioavailable, selective and potent mitogen-activated protein (MAP) kinase kinase (MEK)1 and MEK2 inhibitor. Binimetinib, given in combination with encorafenib, has received marketing approval in several jurisdictions for the treatment of patients with *BRAF*-mutant melanoma as per local prescribing information.

2.3.1 Binimetinib: Clinical Safety

Binimetinib has been administered as a single agent to 943 patients with cancer across multiple studies. The most frequently reported adverse events with single agent binimetinib treatment have been blood creatine kinase elevation, diarrhea, acneiform dermatitis, peripheral edema, rash, nausea and fatigue. The majority of these adverse events have been grade 1-2, with the exception of blood creatine kinase levations, which was seen in 21% at a grade 3-4 level in patients with melanoma and 29% of patients with low grade serous carcinoma of the ovary, fallopian tube, or primary peritoneum.

2.4 Hydroxychloroquine (HCQ)

Chloroquine (CQ) is a synthetic 4-aminoquinoline that has been used for 80 years in humans for malaria prophylaxis and treatment, rheumatoid arthritis, and human immunodeficiency virus (HIV). It is an inexpensive orally available drug that has CNS penetration. It has a large therapeutic index, and its most predictable cumulative toxicity is retinopathy (Marmor et al., 2011). It is this toxicity and worldwide malarial resistance to CQ that lead to discontinuation of extensive research into CQ's non-malarial applications. Chloroquine derivatives such as HCQ are still used extensively in rheumatoid arthritis and lupus erythematosis and have a larger therapeutic index. The chemical structure of CQ derivatives allows them to serve as a weak base which is trapped in acidic cellular compartments (Poole and Ohkuma, 1981). Thus chloroquine derivatives deacidify lysosomes, inhibiting the last step in autophagy. With this last step blocked, a cell reliant on autophagy will increase the generation of autophagosomes and will eventually undergo either apoptotic or non-apoptotic cell death. Evidence in mouse models and human cancer cell lines suggest CQ may have significant anti-tumor activity by inhibiting autophagy induced by cancer therapy (Amaravadi *Cancer Discovery* 2019 PMID:31434711)

2.4.1 Clinical Experience of HCQ in cancer trials

We have previously published the first 6 clinical trials involving combinations of HCQ and cancer drugs (Vogl Autophagy 2014 PMC4203515: Rosenfeld Autophagy 2014 PMC4203513; Rangwala Autophagy 2014 PMC4203514; Rangwala Autophagy 2014 PMC4203516; Mahalingam Autophagy 2014 PMC4203517; Barnard Autophagy 2014 PMC4203518). This effort has demonstrated the safety of the approach in patients with advanced solid tumors. Our preliminary data in 2 phase I studies (presented at the Society of Melanoma Research 2016) demonstrates the safety and striking activity of combined BRAF and autophagy inhibition in BRAF mutant melanoma. We launched a Phase I trial of vemurafenib and HCQ in BRAF^{V600E} melanoma patients (NCT01897116). 7 patients in the 1st dose level (vemurafenib 960 po bid + HCQ 400 po bid) had 2 dose limiting toxicities (DLT; grade 3 rash and grade 3 transaminitis evaluable for response had PR or CR (median max target shrinkage -62% [-38- -100%]). Prolonged PFS was seen in 1 CR (36+ mo) and 1 PR (20 mo). Combined BRAF/MEK inhibition was adopted widely so this trial was closed, the BAMM trial, a Novartis funded multi-institution phase I/II trial of dabrafenib (D), trametinib (T) and HCQ was opened (NCT02257424). Phase I was completed with no DLT (n=7). Recommended phase II dose was HCQ 400 bid with D+T. Phase II enrollment continues. D+T+HCQ was well tolerated, with no evidence of significant ocular toxicity on extensive serial ophthalmological exams (Nti Retina 2018; PMC6039280).

Striking responses were observed: 90% patients have responded and 48% of patients have had an investigator-assessed complete response. Median PFS is roughly 18 months. The only non-responder was found to have *BRAF*^{*V600E*} amplification, and had pyrexia that required frequent dose interruptions.

2.5 Rationale for correlative studies

To test the hypothesis that HCQ could enhance the therapeutic efficacy of B by inhibiting autophagy, this clinical trial will incorporate several correlative studies. First, we will include biopsies before and after starting treatment with HCQ + B. This will allow pathological analysis including electron microscopy by which we can assess the degree of autophagy. This is feasible since the inhibition of the last step of autophagy by HCQ should cause an accumulation of autophagic vesicles that can be detected by electron microscopy and immunoblotting. Next, through serial blood draws, we can investigate non-invasive markers by which autophagic dynamics may be detected. We have selected certain candidate biomarkers such as IL-8, Interleukin-1 Beta, LIF, DKK3, and FAM3C, based on in vitro data that shows elevated serum levels in human patients during high autophagy states (Kraya *Autophagy* 2015 PMC4502670). Finally, we aim to investigate the immune consequences of autophagy inhibition by measuring serum cytokine levels using luminex technology.

For all patients enrolled, we plan to obtain 20 unstained slides from archival FFPE blocks of ideally the latest metastatic lesion that was biopsied will be obtained. IHC assays for correlative autophagy biomarkers: We have identified a 2 gene signature involving Aldehyde dehydrogenase and helicase like transcription factor (HLTF). We have developed IHC protocols for these genes. We hypothesize the patterns of expression of these genes previously identified in HCQ-S and HCQ-R cancer cell lines (Piao Autophagy 2017) will correlate with PFS. In addition, the following proteins will be measured by IHC: Phospho ERK, cleaved caspase 3, PPT1. Additional biomarkers and Immune cell staining will be conducted as the concept is developed further.

3.0 PATIENT SELECTION

3.1 Inclusion Criteria

Each subject must meet all of the following inclusion criteria to be enrolled in the study:

- 1) Metastatic or incurable NSCLC
- 2) Presence of a non-synonymous mutation in KRAS
- 3) Patient must have received at least one prior systemic therapy for metastatic NSCLC or be intolerant/ineligible/refuse available therapies with known benefit
- 4) Ability and willingness to sign a written informed consent document
- 5) Age ≥18 years old
- 6) At least one measureable lesion according to Response Evaluation Criteria in Solid Tumors (RECIST) 1.1
- 7) ECOG performance status 0-1

8) Adequate organ function, as defined below

System	Laboratory Value		
Hematological			
Absolute neutrophil count	>1.250/mcl		
(ANC)			
Platelets	≥100,000/mcL		
Hemoglobin	≥9 g/dL or ≥5.6 mmol/L		
Renal			
Serum creatinine OR	≤1.5 X upper limit of normal (ULN) OR		
Measured or calculated ^a			
creatinine clearance	≥50 mL/min for subject with creatinine levels >		
(GFR can also be used in place	1.5 X institutional ULN		
of creatinine or CrCl)			
Hepatic			
Serum total bilirubin	≤ 1.5 X ULN OR		
	Direct bilirubin ≤ ULN for subjects with total		
	bilirubin levels > 1.5 ULN		
	≤ 2.5 X ULN OR		
AST (SGOT) and ALT (SGPT)	≤ 5 X ULN for subjects with liver metastases		
^a Creatinine clearance should be calculated per institutional standard.			

- 9) Women of childbearing potential must have a negative serum pregnancy test performed within 72hours of the first dose of study therapy. Subjects of reproductive potential must agree to use acceptable birth control methods (see Appendix B for childbearing potential).
- 10) Qtc < 500 mSec on EKG
- 11) Must be able to swallow tablets
- 12) Must be willing to comply with protocol procedures (including completion of diaries and outcome measures

3.2 Exclusion Criteria

A subject will not be eligible for inclusion in this study if the following criteria apply:

- 1) Currently participating in or has participated in a study of an investigational agent or anticipated use of an investigational device within 4 weeks of the first dose of study treatment.
- 2) Untreated symptomatic central nervous system (CNS) metastases and/or carcinomatous meningitis.
- 3) Prior monoclonal antibody within 4 weeks prior to enrollment, or individuals who have not recovered (i.e., ≤ Grade 1 or at baseline) from adverse events due to agents administered more than 4 weeks earlier.
- 4) Known additional malignancy that is progressing or requires active treatment. Exceptions include basal cell carcinoma of the skin, squamous cell carcinoma of the skin, non-invasive bladder tumors, or in situ cervical cancer
- 5) Active infection requiring systemic therapy with IV antibiotics

- 6) History or current evidence of any condition, therapy, or laboratory abnormality that might confound the results of the trial, interfere with the subject's participation for the full duration of the trial, or is not in the best interest of the subject to participate, in the opinion of the treating investigator.
- 7) Known psychiatric or substance abuse disorders as documented in the chart that, in the opinion of the investigator, would interfere with cooperation with the requirements of the trial.
- 8) Pregnant or breastfeeding women
- 9) Anticipated receipt of any live vaccine within 30 days prior to the first dose of trial treatment.
- 10) Have a known immediate or delayed hypersensitivity reaction or idiosyncrasy to drugs chemically related to study drug, or excipients or to dimethyl sulfoxide (DMSO).
- 11) Patients receiving cytochrome P450 enzyme-inducing anticonvulsant drugs (EIADs) (i.e. phenytoin, carbamazepine, Phenobarbital, primidone or oxcarbazepine) within 4 weeks of the start of the study treatment
- 12) Known Hepatitis B Virus (HBV), or Hepatitis C Virus (HCV) infection (subjects with laboratory evidence of cleared HBV and/or HCV will be permitted)
- 13) Patients with a previously documented retinal vein occlusion.
- 14) History or evidence of increased cardiovascular risk including any of the following:
 - Current clinically significant uncontrolled arrhythmias.

Exception: Subjects with controlled atrial fibrillation for > 30 days prior to randomization are eligible.

- History of acute coronary syndromes (including myocardial infarction and unstable angina), coronary angioplasty, or stenting within 6 months prior to randomization.
- Ejection fraction of ≤50% as measured by echocardiography or MUGA
- 15) Any other conditions judged by the investigator that would limit the evaluation of the subject.

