11.4 Simon 2-stage Design

After treatment with standard of care chemotherapy or chemo-immunotherapy, the standard of care for the treatment of progressive NSCLC is docetaxel. The ORR to docetaxel is 14% (Garon et al Lancet 2014). This experimental regimen will be considered not worthy of further development if the ORR is 10% (clearly inferior to docetaxel) and considered worthy of further development if the ORR is 30%.

- Stage 1: Ten patients will be entered into the first stage of the study. If 1 or fewer of these 10 patients respond, then the trial will be terminated. If at least 2 of these 10 patients respond, then proceed to Stage 2.
- Stage 2: Nineteen additional will be entered (total of 29) into the second stage of the study. If 5 or fewer of the 29 patients respond, then it will be concluded that the regimen does not merit further investigation. If 6 or more of the 29 patients respond, then it will be concluded that the regimen does merit further investigation.

The trial is designed with the following characteristics:

- False positive error: If the true response rate is 10%, then the probability of recommending the regimen for further investigation, is no more than 0.05.
- Power: If the true response rate is 30%, then the probability of recommending the regimen for further investigation, is at least 0.80.
- If the true response rate is 10%, then the probability of early termination (PET) is 0.74 after 10 patients have been treated.

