11.5 Plans for Data Analysis

Primary

- The objective response rate and 95% exact confidence interval will be calculated.
- All observed toxicities will be graded and tabled (worse grade experienced in all cycles). The
 overall rate of > grade 3 toxicity and 95% exact confidence interval will be calculated.

Secondary

• Progression-free survival and overall survival will be estimated by the method of Kaplan and Meier. Median values and 95% confidence intervals will be calculated.

Exploratory

- Associations between objective response and expression of biomarkers pre-treatment will be tested using nonparametric Wilcoxon rank sum test. Comparisons of pre- and post-treatment biomarker expression will be conducted using Wilcoxon signed ranks test for paired data.
- Describe autophagic vesicles/cell in tumor tissue at various time points using descriptive statistics and scatter plots.
- To evaluate HCQ pharmacokinetics and pharmacodynamics to determine whether changes in blood-based autophagy biomarkers (ctDNA KRAS allelic frequency) reflect tissue-based changes in autophagy (autophagic vesicles/cell), the nonlinear mixed–effects modeling approach (NONMEM) will be used to perform a full population PK analysis. PK-PD analyses to be conducted by University of Sciences of Philadelphia. Analysis methods – See Section 18. The key variables for the population include the Cmax and half life. Population PK will be assessed and qualitatively compared to population PK findings from other HCQ studies. No hypothesis testing will be performed for any of the vairables.

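### Exclusion 3 requires toxicity recovery only for agents given more than 4 weeks earlier, and commercial chemotherapy and small-molecule drugs have no washout, so carry-over can enter both primary endpoints

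*Combined protocol and SAP*

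**What the plan says.** **Washouts (Section 3.2).** Two timed anti-cancer washouts are stated. Item 1 excludes a patient who has "participated in a study of an investigational agent or anticipated use of an investigational device within 4 weeks of the first dose". Item 3 excludes "Prior monoclonal antibody within 4 weeks prior to enrollment". The first is anchored to first dose and the second to enrollment. No interval is given for commercial chemotherapy, small-molecule targeted drugs or radiotherapy.

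**Recovery.** The second half of item 3 excludes patients who have "not recovered (i.e., ≤ Grade 1 or at baseline) from adverse events due to agents administered more than 4 weeks earlier". No other criterion requires recovery from earlier treatment.

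**Prior therapy.** Inclusion 3 reads "Patient must have received at least one prior systemic therapy for metastatic NSCLC or be intolerant/ineligible/refuse available therapies with known benefit". It sets no interval since the last dose and does not require progression on the last therapy. Section 11.4 sets the trial's context as "After treatment with standard of care chemotherapy or chemo-immunotherapy".

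**Backstops.** Exclusion 6 covers "any condition, therapy, or laboratory abnormality that might confound the results of the trial", in the treating investigator's opinion. Exclusion 15 covers other conditions that the investigator judges would limit evaluation. Organ-function limits apply (Section 3.1), with screening laboratory tests within 10 days before Cycle 1 Day 1 (Section 8.0, note 11). Section 4.1 bars other anti-cancer treatment alongside the study drugs.

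**Baseline.** Note 8 of the study calendar allows the baseline scan up to 30 days before Cycle 1 Day 1, while Section 9.3 allows no more than 4 weeks. Partial response is measured against that baseline sum (Section 9.4.1).

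**The concern.** A recovery rule normally reaches the most recent treatment, because that is where unresolved toxicity is most likely. This one leaves it out. The rule covers agents given more than 4 weeks earlier, while the only more recent drugs caught by a washout are antibodies and investigational agents. A patient just off commercial chemotherapy falls between the two.

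The trial has no control arm to separate the late effect of the previous drug from the effect of binimetinib plus hydroxychloroquine. Two routes are open:

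- **ORR.** Tumour shrinkage from a drug given shortly before the baseline scan, or between that scan and day 1, would be scored as response to the study regimen. Inclusion 3 also admits patients intolerant of available therapy, who may have stopped treatment for toxicity rather than progression.
- **Grade 3 or higher toxicity rate.** Delayed effects of the previous drug that first appear or worsen after day 1 would be counted.

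At stake are the 2-of-10 gate, the 6-of-29 decision rule and the primary safety estimate.

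**Working it through.** **1. Exclusion 3 applied to two patients.** Both have the same unresolved grade 2 non-laboratory toxicity from commercial chemotherapy, above their baseline.

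- Last dose 5 weeks ago: the agent was given more than 4 weeks earlier, so the patient is excluded.
- Last dose 1 week ago: the recovery clause does not apply, and neither the antibody nor the investigational-agent washout applies. Exclusion 3 does not exclude the patient. Only exclusions 6 and 15, at the investigator's discretion, could.

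**2. The plan's own design figures.** Inputs from Section 11.4: 10 patients in Stage 1, continue with at least 2 responses; 19 more in Stage 2; positive with at least 6 of 29; ORR 10% (not worthy) and 30% (worthy).

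- P(stop early at 10%) = 0.9^10 + 10 × 0.1 × 0.9^9 = 0.3487 + 0.3874 = 0.736. The plan states 0.74.
- P(open Stage 2) = 1 − 0.736 = 0.264.
- P(recommend) = Σ over x = 2 to 10 of P(X1 = x) × P(X2 ≥ 6 − x), with X1 ~ Bin(10, p) and X2 ~ Bin(19, p).
- At p = 0.10 this is 0.0471 (plan: no more than 0.05). At p = 0.30 it is 0.8051 (plan: at least 0.80).

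The design figures reproduce and are not in dispute.

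**3. Sensitivity to carry-over.** The documents give no carry-over rate, so each case below is an assumption. The true ORR of the regimen is 10% throughout.

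| Assumed carry-over | P(open Stage 2) | P(recommend) |
|---|---|---|
| None | 0.264 | 0.047 |
| Adds 2 points (p = 0.12) | 0.342 | 0.095 |
| Adds 5 points (p = 0.15) | 0.456 | 0.201 |
| One certain carry-over responder in the first 10 | 0.613 | 0.128 |
| One certain carry-over responder in each stage | 0.613 | 0.244 |

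Rows 2 and 3 put the raised p into the formulas of step 2. In row 4, one of the ten is already a responder, so Stage 2 opens if at least one of the other nine responds: 1 − 0.9^9 = 1 − 0.3874 = 0.613.

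**4. Safety endpoint.** One extra carry-over event moves the grade 3 or higher rate by 1/10 = 10 points at n = 10, or 1/29 = 3.4 points at n = 29. For example, the exact 95% interval goes from 5.8% to 35.8% (5/29) to 8.0% to 39.7% (6/29).

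**The case against.** The strongest defence is that several rules already narrow both routes.

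- **Discretion.** Exclusion 6 names therapy that might confound the results, and exclusion 15 adds a further judgement. One cannot say that a recently treated patient meets every stated criterion. But these items give no interval and no drug class, so they reduce the gap without closing it.
- **Response is hard to carry over.** It needs a 30% reduction from baseline, with confirmation at least 4 weeks later (Sections 9.0 and 9.4.3). Section 11.4 speaks of progressive disease, where shrinkage from the failed drug is less plausible. This lowers the likely rate. However, inclusion 3 does not require progression, and a drug given after the baseline scan has its whole effect measured against that scan.
- **Size.** Assuming a certain carry-over responder shows that a 2-of-10 gate is fragile. It does not show how often this eligibility text would produce one. That is correct, and the figures are illustrations only.

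Three stronger readings might be inferred, and the documents do not support them:

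- Lesions irradiated before the baseline scan do not feed the ORR. Section 9.2 makes lesions in a previously irradiated area non-measurable. For target lesions, only radiotherapy between the scan and day 1 remains a route.
- Stable residual toxicity does not count in the grade 3 or higher rate. An adverse event must develop or worsen on study (Section 10.1), and a pre-existing condition is reported only if it worsens (Section 10.3.5). The organ-function limits also screen out part of the laboratory toxicity.
- A uniform 4-week washout does not follow. The documents set that interval only for antibodies and investigational agents.

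**Conclusion.** The point holds in a bounded form. The recovery clause in exclusion 3 omits the most recent agents, and commercial chemotherapy and small-molecule drugs have no washout. Only the organ-function limits and investigator discretion stand between recent treatment with such drugs and entry. Late shrinkage from such a drug, and new or worsening delayed toxicity, can therefore enter the two primary endpoints.

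The size is unknown, because it depends on how many patients enrol soon after such treatment and how often a carry-over effect meets the response or grade 3 threshold. What can be said is that the stated false-positive limit has little slack: 0.047 against 0.05, so carry-over worth only 2 points of ORR takes it to 0.095. The sample size and decision boundaries need no change. This should be amended; it does not invalidate the design.

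**What to change.** Amend the eligibility and imaging text:

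1. Make the recovery clause in exclusion 3 apply to adverse events of any prior anti-cancer therapy, whenever given, keeping the existing grade and baseline wording.
2. Have the sponsor state a washout for chemotherapy and for small-molecule targeted drugs, with the interval chosen and justified by class. No interval is proposed here.
3. Require that no anti-cancer drug and no radiotherapy to a target lesion be given between the baseline scan and first dose, or that the scan be repeated if one is given.
4. Anchor all washouts to first dose; items 1 and 3 now use different anchors.
5. Reconcile the 30-day scan window in the study calendar with the 4-week limit in Section 9.3.

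The cost is a short amendment. Some patients will start later, and some with lasting toxicity will qualify only through the baseline alternative in the recovery clause. If the amendment removes carry-over, the operating characteristics in Section 11.4 apply as stated.
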